5.0 Work stream 2: Feasibility study

The feasibility study will pilot efficient research methods for an implementation study of VTE risk-assessment tools and estimate key parameters for study design. The implementation study design will be determined by the findings of the evidence synthesis but is likely to involve either a cluster design in which wards or hospitals are allocated to alternative risk-assessment strategies or an observational design in which hospitals using different strategies are compared. The study population, setting, health technologies being assessed and outcomes are likely to be those defined above, with the primary outcome being any clinically-relevant VTE. The feasibility of such a study will depend upon our ability to undertake efficient intervention and outcome data collection from a large study population.

The feasibility study will involve an iterative process of developing and testing data collection methods but ultimately aims to determine the feasibility of (1) using routine administrative data to measure VTE and bleeding outcomes, and (2) collecting standardised VTE risk assessment data as part of routine practice. The feasibility study will be an observational study. We will not attempt to change practice or implement any risk-assessment methods. The target population, health technology and outcomes of interest are as defined in the overview of the research plan above.

Objective 1 will be addressed by determining whether routine administrative data sources correctly code VTE or bleeding events, verified by review of hospital records. The reference standard for this assessment will be based on expert review of identified cases, using the outcome definitions provided above.

Objective 2 will be addressed by determining the proportion of cases in which each key risk predictor is routinely recorded in a standardised risk assessment. The key risk predictors will be selected and defined by an expert panel drawing upon items used in existing risk-

assessment tools and their expert clinical knowledge. The PPI members of the research team will work with representative groups to review the acceptability of using each risk predictor to determine whether prophylaxis is given.

5.1 Selection of participants

The study will be undertaken initially in Salford Royal Hospital and a second NHS hospital acting as a pilot site. We will select wards at each hospital covering medical, surgical and trauma admissions. The participants will be all inpatients requiring assessment for VTE risk and will be entered into the study base on the following criteria:

Inclusion criteria

1. Hospital inpatients, including medical, surgical and trauma patients, requiring assessment for VTE risk

2. Patients aged 16 and over

Exclusion criteria

- 1. Pregnant/postpartum women
- 2. Children under the age of 16 years

3. Patients admitted to a critical care environment defined as level 2 or above

The study will not change patient care and only members of the clinical team will access personal data, so we will not seek individual patient consent to participate.

We will subsequently identify two additional hospitals to determine whether the data collection methods developed in the two initial sites can be applied elsewhere and ensure that findings are more generalizable.

Initially we will seek Research Ethics Committee (REC) approval to only use anonymised data, so that only members of the clinical team (including research nurses) are able to access personal data. During the study we will explore whether and how this restriction limits our ability to collect and link the necessary risk-assessment and outcome data. If we are limited to the extent that a case can be made for using personal data without consent, we will apply to the Confidentiality Advisory Group (CAG) of the Health Research Authority for appropriate approval and/or to test the case for approval in a definitive study. Throughout this process we will work with our PPI representatives to consult PPI groups (SECF, Thrombosis UK and hospital-based PPI groups) to determine patient and public views on the acceptability of using data in this way for research.

We will also undertake a national survey of VTE leads at acute NHS hospitals across the UK to determine (1) current practice regarding VTE risk-assessment and use of prophylaxis at their hospital, (2) methods used to record VTE risk-assessment data, and (3) willingness to participate in an implementation study of risk-assessment tools. Current practice will be determined by asking respondents to provide hospital VTE prophylaxis guidance and any other relevant information. Willingness to participate will be explored through survey questions asking whether they consider the hospital would be able to take part in an observational study or a cluster randomised study, in which the whole hospital or individual wards would be randomised.

5.2 Data collection

Piloting of data collection methods will take place over 11 months but this will initially be an intermittent and iterative process, during which data collection methods will be developed, tested, reviewed and revised at two sites, and then introduced at two additional sites. This will culminate in a 2-month period of continuous data collection across four hospitals, during which the developed process will be formally tested.

Routine practice requires recording of VTE predictors for all inpatients. We will identify how data are recorded and what items are recorded, and then compare this to data requirements for existing risk-assessment tools and any other potentially important VTE risk predictors.

We will explore whether augmenting or standardising routine data recording can improve the scope and quality of data recorded, using electronic methods wherever possible. We will also explore whether VTE risk factors are recorded through hospital information systems, either for VTE risk-assessment or for general data collection. If so, we will explore processes for extracting and linking relevant data items. We will therefore determine and optimise the scope of risk-assessment variables that can be routinely recorded in a standardised manner.

In the final 2-month period we will pilot the methods we have developed to test the completeness of recording of predictor variables and our ability to calculate existing risk assessment scores from the collected data.

The main outcome measures are defined in the overview of the research plan. The primary outcome for any future implementation study will be clinically important VTE, defined as diagnostic coding of any VTE event during hospital attendance or admission, or recording of VTE as a cause of death, up to 90 days after initial risk assessment.

An implementation study of risk-assessment tools will need to link risk-assessment data collected at hospital admission to routinely collected outcome data, such as HES. These data can be accessed through the hospital providing the data or through NHS Digital. Both routes require personal details, such as a hospital number or NHS number, to allow accurate linkage to risk-assessment data. Research nurses can access data through the hospital but this approach may miss events occurring after discharge and presenting to another hospital. Accessing data through NHS Digital using personal details would require CAG approval.

To determine the validity of efficient methods for identifying outcomes we will undertake case note review of all events identified through routine data sources and a sample of cases with no event identified. Research nurses will review hospital records and record details of any outcome events up to 90 days and enter the data on to a standardised Case Report Form (CRF). Two independent experts will then review anonymised data collected on the outcome events and determine whether they are classified as outcomes according to definitions determined by an independent adjudication panel. Discordant judgements will be resolved through discussion and, if appropriate, independent assessment by a third reviewer.

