- 3. Determine the value of information provided by future research
- 4. Determine the feasibility of using efficient methods in a future implementation study of VTE risk assessment tools

Methods

We plan to undertake evidence synthesis and piloting of efficient primary research methods. The target population is hospital inpatients, including medical, surgical and trauma patients but excluding critical care patients, children and women admitted to hospital for pregnancy-related reasons. The health technologies being assessed are risk assessment tools that use clinical information to select patients with an increased risk of VTE for prophylaxis. The outcomes of interest are VTE (deep vein thrombosis (DVT) and pulmonary embolism (PE)) and bleeding events.

Work stream 1 (evidence synthesis) will update existing systematic reviews to identify riskassessment tools and estimate their prognostic accuracy. Decision-analytic modelling will then simulate the management of a cohort of hospital inpatients and compare strategies using risk-based prophylaxis to prophylaxis for all or prophylaxis for none. We will estimate VTE events, bleeding events, quality-adjusted life-years (QALYs) and costs associated with each strategy and then estimate the incremental cost per QALY gained by each strategy compared to the next most effective alternative on the efficiency frontier. We will then estimate the expected value of information of further primary research.

Work stream 2 (feasibility study) will involve an observational study of 3000 inpatients across four NHS hospitals to develop efficient methods for a future implementation study. We will not attempt to change practice or implement any risk-assessment methods. We will pilot the collection of standardised VTE risk-assessment data in routine clinical practice and the use of linked Hospital Episodes Statistics and Office for National Statistics (ONS) mortality data for outcome measurement. We will then test the completeness of linkage and review case notes of patients to determine the accuracy of routine data.

Timelines for delivery

Year 1: Systematic reviews, decision analysis modelling, value of information analysis; prepiloting, ethical and regulatory approvals

Year 2: Write-up and dissemination of secondary research; data collection, analysis and reporting of primary research

Anticipated impact and dissemination

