5.4 Sample size

The sample size is only estimated for the 2-month pilot phase in which we test the data collection methods. The initial iterative developmental phase will collect data in each cycle until a reasonably reliable conclusion can be drawn regarding the issue of interest. The broad inclusion criteria and lack of requirement for consent means that there are few practical limitations to patient numbers.

We plan to identify 3000 inpatients over 2 months across 4 hospitals. This will allow key parameters to be estimated with a high degree of precision across the whole cohort (standard error <1%) and an acceptable degree of precision in specific patient groups.

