11.0 Ethics

The evidence synthesis work stream will only use secondary research methods, carries no significant ethical risk and therefore does not require ethical approval. The feasibility study work stream only involves observational methods, with no change to patient care, so ethical risks are low and mainly related to patient confidentiality and data protection.

The main ethical issue relates to using patient data without consent. This is justified, both ethically and with regard to General Data Protection Regulations, on the basis of medical research in the public interest. An implementation study requires a large, unselected patient population that includes all people at risk of VTE. It would therefore not be feasible to seek patient consent to use their data and the ethical risks of causing distress and confusion by seeking consent for secondary data use would outweigh the ethical benefits. We will only use anonymised data in the analysis and will put in place a process to minimise the risks to patient confidentiality.

As outlined in the data collection section, we will explore using standardised, routinelyrecorded risk-assessment information. This is collected by the clinical team as part of routine care and will be extracted by research nurses in the participating hospitals. Only anonymised details will be used by the research team. However, we will need to link risk-assessment data to outcomes recorded in routine clinical coding used to generate Hospital Episodes Statistics and then review hospital records to determine the accuracy of the clinical coding. We will explore whether this can be feasibly done within the hospital or whether personal data need to be used to link with data collected nationally by NHS Digital.

In the first six months of the project we will secure Research Ethics Committee approval and HRA approval to undertake the feasibility study. Initially this will be on the basis of only members of the clinical care team (including research nurses) using personal data. If this does not allow data linkage to support an efficient study, we will seek CAG section 251 approval to use personal data to link hospital data with NHS Digital data.

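### Unless national HES/ONS linkage is obtained, criterion 3 cannot detect VTE presenting to another hospital or VTE deaths outside hospital, and the section 5.3 event rate is likely to be an undercount

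*Protocol*

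**What the plan says.** **Outcome.** Section 5.2 defines the primary outcome of a future implementation study as coded VTE at a hospital attendance or admission, "or recording of VTE as a cause of death, up to 90 days after initial risk assessment". It does not restrict this to the participating hospital. Section 5.3 plans to estimate the rate of this outcome from the 2-month pilot.

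**Routes to routine outcome data.** Section 5.2 names two, the hospital itself and NHS Digital. Of the first it says: "Research nurses can access data through the hospital but this approach may miss events occurring after discharge and presenting to another hospital". The second, if personal details are used, needs Confidentiality Advisory Group (CAG) approval. Sections 5.1 and 11.0 start with personal data confined to the clinical team. Section 11.0 then adds: "If this does not allow data linkage to support an efficient study, we will seek CAG section 251 approval".

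**Reference standard.** Section 5.2: "Research nurses will review hospital records and record details of any outcome events up to 90 days". All routine-data events and a sample of non-events are reviewed. Criterion 2 is the share of routine-data events confirmed by the review (target 100%). Criterion 3 is the share of routine-data non-events in which the review finds an event (target 0%).

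**Summary of Research, Methods.** The study will pilot "the use of linked Hospital Episodes Statistics and Office for National Statistics (ONS) mortality data for outcome measurement", and: "We will then test the completeness of linkage and review case notes of patients to determine the accuracy of routine data".

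**What section 5 and later sections do with that.** Section 5 does not mention ONS. None of the six criteria in section 5.3 measures linkage completeness. Section 7.0 bars access to identifiable data by anyone outside the clinical care team. Section 16.2 refers to the section 5.3 list as the criteria for feasibility.

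**The concern.** A reference standard can reveal missed events only if it sees something that the index source does not. On the local route, both sources appear to be the participating hospital's: its clinical coding and its case notes. The Protocol acknowledges that the first may miss events presenting elsewhere, but describes no access for the second to another hospital's records or to death registration.

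Two results of the feasibility study are affected. Criterion 3 could be reported as met, and read as evidence that routine data capture the outcome, when it shows only that local coding agrees with local notes. The event rate would go forward as a design parameter for the implementation study. Section 3.1 describes that rate as relatively low, and gives this as the reason a large study is needed for adequate power.

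The Summary of Research offers the one measure that would expose the gap, a test of linkage completeness. Because section 5.3 has no matching criterion, the study could finish without saying whether this was tested.

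**Working it through.** **1. The plan's own precision figure.** Section 5.4: "We plan to identify 3000 inpatients over 2 months across 4 hospitals", giving "standard error <1" per cent for the whole cohort. The largest binomial standard error is √(0.25/3000) = 0.913%, so the figure reproduces. It describes sampling error only and says nothing about events that neither source can see.

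**2. Are both sources local?** Taken together:
- sections 5.1 and 11.0: at first only the clinical team, including research nurses, uses personal data;
- section 5.2: the nurses obtain outcomes through the hospital and review hospital records;
- section 7.0: no identifiable access outside the clinical care team.

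The inference is that, without national linkage, coding and notes are both the participating hospital's. The Protocol does not state this in so many words.

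**3. What criterion 3 then measures.** Let N be the number of patients, p the true 90-day event rate and f the share of events absent from both sources. Suppose every other event is correctly coded. Then:
- events lost = N·p·f
- observed criterion 3 = 0%, for any f
- true criterion 3 = N·p·f / [N − N·p·(1 − f)]
- true sensitivity = 1 − f
- apparent event rate = p·(1 − f)

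N = 3000 comes from section 5.4. The Protocol gives neither p nor f, so both are assumptions, shown as a range.

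| Assumed p | Events | Assumed f | Lost | Criterion 3 observed | Criterion 3 true | Sensitivity | Apparent rate |
|---|---|---|---|---|---|---|---|
| 0.5% | 15 | 10% | 1.5 | 0% | 0.05% | 90% | 0.45% |
| 0.5% | 15 | 40% | 6 | 0% | 0.20% | 60% | 0.30% |
| 1% | 30 | 10% | 3 | 0% | 0.10% | 90% | 0.9% |
| 1% | 30 | 20% | 6 | 0% | 0.20% | 80% | 0.8% |
| 1% | 30 | 40% | 12 | 0% | 0.40% | 60% | 0.6% |
| 2% | 60 | 10% | 6 | 0% | 0.20% | 90% | 1.8% |
| 2% | 60 | 40% | 24 | 0% | 0.81% | 60% | 1.2% |

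For p = 1% and f = 20%: 3000 × 0.01 × 0.20 = 6 lost, and 6/(3000 − 24) = 6/2976 = 0.20%.

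**4. Would a larger review sample help?** No. In that case, reviewing all 2976 apparent non-events still gives 0. The exact two-sided 95% upper limit is 1 − 0.025^(1/2976) = 0.12%, which lies below the true 0.20%. More review tightens the interval around the wrong value.

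**5. Size against sampling error.** At p = 1% the standard error of the rate is √(0.01 × 0.99/3000) = 0.18%. The undercount is 0.2 percentage points at f = 20% and 0.4 at f = 40%, so about one to two standard errors. The planned confidence interval does not allow for it.

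**6. With national linkage.** Outside admissions and registered VTE deaths would be in the routine data and would no longer be hidden from it. A review of local notes might then fail to confirm them, which would lower criterion 2 instead. The problem in step 3 therefore depends on the route.

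**The case against.** The strongest reply is that national linkage is part of the plan. Sections 5.1, 5.2 and 11.0 set out the CAG and NHS Digital route, the section 9.0 timetable has rows for CAG approvals and for piloting record linkage, section 16.2 discusses linkage as a barrier, and the Summary of Research names HES and ONS data. This stands. A reader might infer that outside events are invisible on any route, but the documents do not support that, and section 5.2 says only that the hospital route may miss them. Local notes may mention some outside events. Those would raise criterion 3 above 0%, but the events that leave no local trace would still not count.

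Second, section 5.0 frames the first feasibility objective as whether routine sources code events correctly, checked against hospital records. As coding validation, criteria 2 and 3 do their job. This also stands, but the same section states the wider aim as measuring outcomes with routine data, and section 5.3 estimates the event rate from the same pilot. Coding accuracy alone supports neither.

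Third, a reader might infer that the decision to seek CAG approval hangs on criterion 3. It does not: sections 5.1 and 11.0 tie it to whether restricted access limits data collection and linkage. Nor does any rule say that 0% on criterion 3 makes hospital-only data adequate. Making the CAG decision wait for measured out-of-hospital capture would be circular, because on the Protocol's account the route to those data with personal details itself needs CAG approval.

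Fourth, labels and sensitivity tables are often left to a statistical analysis plan. That is fair for presentation. It does not cover the success criteria, which the Protocol fixes itself.

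**Conclusion.** The point holds, conditional on national linkage not being obtained. On the local route, criterion 3 is wrong as written as a measure of missed primary-outcome events, because it cannot register VTE presenting to another hospital or VTE deaths outside hospital that leave no local record. The event rate from that route is likely to be an undercount.

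The size is unknown. The table rests on assumed event rates of 0.5% to 2%, assumed losses of 10% to 40% and perfect coding of all other events. A reader might be tempted to quote a specific percentage of VTE lost, but the documents give no basis for one. The conclusion also rests on the inference that only the participating hospital's records are reviewed.

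Separately, and whichever route is used, the Summary of Research promises linked HES and ONS mortality data and a linkage-completeness test. Section 5 is silent on ONS, section 5.3 has no such criterion, and the unqualified bar in section 7.0 sits uneasily with the conditional use of personal data in section 11.0. These passages need to be reconciled.

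**What to change.** - **Section 5.3, criteria 2 and 3.** State that under the local route they measure coding accuracy for events presenting to the participating hospital only, and that meeting them does not show complete outcome capture.
- **Section 5.3, event rate.** Report the confirmed local-route rate as a likely undercount of the 90-day primary outcome, with a sensitivity range whose inputs are labelled as assumptions.
- **Section 5.3, new criterion.** Add the completeness test promised in the Summary of Research: the proportion of patients linked to national HES and ONS data. Report it if linkage is obtained; otherwise declare it not tested.
- **Sections 5.1 and 11.0.** Treat the gap already admitted in section 5.2 as a reason to seek CAG approval, and state that a satisfactory criterion 3 is not evidence against needing national linkage.
- **Consistency.** Reconcile the Summary of Research, section 5, section 7.0 and section 11.0 on ONS data, linkage and who may access identifiable data.

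The cost is wording, a sensitivity table and one extra proportion if linkage is obtained, with no added patients. The downside is a narrower conclusion about outcome capture until linkage is in place.

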3.6 Outcomes

DVT: a filling defect identified by ultrasound or venography or CT scan, or a positive image on MR direct thrombus imaging, within the inferior vena cava, common iliac, internal iliac, external iliac, common femoral, superficial femoral, popliteal trifurcation, posterior tibial, peroneal, gastrocnemius or soleal veins of the leg.

Clinically detected DVT: a DVT with symptoms of leg pain, swelling or discolouration that is identified during routine patient care.

Screening-detected DVT: a DVT, with or without symptoms, that is not identified during routine patient care but is detected if radiological screening is undertaken.

PE: a filling defect reported to be pulmonary embolism found on CT pulmonary angiography or digital subtraction angiography in a branch of the pulmonary artery. Or else a high probability perfusion or ventilation-perfusion scan.

Major bleeding: as defined by the International Society of Thrombosis and Haemostasis (Schulman 2005).

Clinically relevant non-major bleeding: as defined by International Society of Thrombosis and Haemostasis (Schulman 2005).

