5.3 Data analysis

The following criteria will be used to determine success:

- 1. Ethical and regulatory approval for proposed methods
- 2. Proportion of outcome events identified by routine data sources that are confirmed by record review (target 100%)
- 3. Proportion of cases with no outcome event identified by routine data sources that have an event identified on record review (target 0%)
- 4. Proportion of inpatients with data collected (target 90%)
- 5. Proportion of each predictor variable recorded (target 90%)
- 6. Proportion of each risk assessment tool completed using available data (target 90%)

We will also estimate key parameters for any future implementation study:

- 1. The primary outcome event rate
- 2. Event rates for other outcomes
- 3. The proportion receiving prophylaxis in current practice
- 4. The proportion who would receive prophylaxis if alternative risk assessment tools were used

Descriptive analysis will report proportions, with a 95% confidence interval, from the 2-month pilot phase.

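### The sample meant to reveal uncoded VTE has no fixed size or selection; a simple sample of a few hundred notes would probably find 0 to 2 cases, so it should be stratified by imaging.

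*Protocol*

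**What the plan says.** Section 5.0 makes the use of routine administrative data to measure VTE and bleeding the first aim of the feasibility study. The reference standard there is expert review of hospital records, "using the outcome definitions provided above".

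Those definitions, in section 3.6, rest on imaging. DVT is "a filling defect identified by ultrasound or venography or CT scan", or a positive MR thrombus image, in named veins. PE is a filling defect on CT pulmonary angiography or digital subtraction angiography, or a high-probability lung scan.

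Section 5.2 plans "case note review of all events identified through routine data sources and a sample of cases with no event identified". It says nothing on how many patients without a coded event are reviewed or how they are chosen.

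Section 5.3 lists the proportion of such patients found to have had an event as success criterion 3, with a target of 0%. It adds: "Descriptive analysis will report proportions, with a 95% confidence interval, from the 2-month pilot phase".

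The only statement on size, in section 5.4, concerns the whole cohort: "We plan to identify 3000 inpatients over 2 months across 4 hospitals", with a standard error below 1%.

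**The concern.** Coding can fail in two ways. False positives are dealt with, because every coded event is reviewed. False negatives can be found only in the sample of patients with no coded event. Section 3.1 itself calls the rate of symptomatic VTE relatively low, so a sample of practical size taken without regard to imaging would hold very few missed VTE.

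Criterion 3 could then read 0% and look met while coding misses much of the VTE. The outcome intended for the implementation study is coded VTE or VTE recorded as a cause of death (section 5.2). If under-coding cannot be estimated, the feasibility study cannot say whether that outcome is fit for use. Which notes are pulled is decided in the field and cannot be repaired at analysis.

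**Working it through.** **The plan's own figure.** The standard error of a proportion is √(p(1−p)/N). At the worst case, p = 0.5 and N = 3000, it is √(0.25/3000) = 0.91%, so the stated bound below 1% is correct. It applies to the cohort and not to the sample of patients with no coded event.

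**Inputs.** From the protocol: 3000 patients, imaging-based definitions and a 95% interval. Assumed, because the protocol gives no figure: VTE rate 1% (range 0.5% to 3%), coding capture 50% to 90%, 300 notes reviewed (range 100 to 1000), and every coded event confirmed. The 1.0% under Existing literature is a modelled treatment threshold, not an event rate.

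**Formulas.** Missed VTE = 3000 × rate × (1 − capture). Coded-negative patients = 3000 − 3000 × rate × capture. Expected found = notes × missed / coded-negatives. Probabilities are hypergeometric.

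**Simple sample of 300 notes, 1% VTE (30 cases):**

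| Capture | Coded | Missed | Coded-negative | True criterion 3 | Expected found | P(none) | P(0 to 2) |
|---|---|---|---|---|---|---|---|
| 50% | 15 | 15 | 2985 | 0.50% | 1.5 | 20% | 81% |
| 70% | 21 | 9 | 2979 | 0.30% | 0.9 | 38% | 95% |
| 90% | 27 | 3 | 2973 | 0.10% | 0.3 | 73% | 99.9% |

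**Varying the inputs.**
- At 1% VTE and 80% capture (6 missed among 2976), the expected number found is 0.2, 0.6, 1.0 and 2.0 for 100, 300, 500 and 1000 notes.
- At 300 notes it is 0.15 (0.5% VTE, 90% capture), 1.2 (2%, 80%), 3.0 (2%, 50%) and 4.6 (3%, 50%).

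**What a result of zero would mean.** For 0/300 the exact two-sided 95% upper limit is 1 − 0.025^(1/300) = 1.22%. Times 2976 coded-negatives, that is about 36 missed VTE. With 24 coded events, the lower limit for capture is 24/(24 + 36.4) = 40%.

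**What one case would mean.** With 21 coded events, 1/300 scales to 2979/300 = 9.9 missed, so capture is 21/30.9 = 68%. The exact limits for 1/300 (0.0084% to 1.84%) give 0.25 to 54.9 missed, so capture lies between 28% and 99%.

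**Stratifying by imaging.** If 5%, 10% or 15% of 2979 coded-negatives had relevant imaging (assumed), the imaged stratum is about 149, 298 or 447 notes; at 20% it is about 596. Reviewing all of it finds all 9 missed VTE that meet section 3.6 and are visible locally. Capture is then 21/30 = 70%, exact 95% interval 51% to 85%.

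**Limit of that gain.** The interval treats the non-imaged stratum as holding no missed VTE, which is true by definition under section 3.6. If a random sample of that stratum is instead weighted up, then with 10% imaged about 2680 patients remain. Finding 0 in 50 (upper limit 7.1%) allows about 190 further events, and 0 in 300 (1.22%) allows about 33.

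**The case against.** **Selection is unstated.** A reader might infer that the sample is untargeted. Section 5.2 does not say so; it is silent, it describes methods as still being developed, and detail may lie in an analysis plan not shown. That stands. The figures above describe a simple sample, which the text permits but does not require.

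**The yield depends on assumptions.** This also stands. It is not a property of the protocol that the sample finds one case or none: 2 are expected in 1000 notes at 80% capture, and 3 to 5 in 300 notes at 2% to 3% VTE with half uncoded.

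**Not every missed VTE need lie among a few imaged patients.** That stronger reading is tempting, but the documents do not support it outright:
- Section 5.2 also refers to definitions set by an adjudication panel, which may differ from 3.6.
- Its outcome for the future study includes VTE as a cause of death, which needs no imaging.
- It warns of events presenting to another hospital, whose imaging would not be in the local record.
- Section 3.6 accepts a filling defect on CT, so scans done for other reasons could count. No figure shows that the imaged are few.

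**Criterion 3 is not capture.** A simple random sample estimates criterion 3 without bias, and section 5.3 does not list capture. True, but criterion 3 runs only from 0.10% to 0.50% as capture falls from 90% to 50%, so it barely separates good coding from poor.

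**The sample must also serve bleeding.** This stands, and it is why a random component has to remain.

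**Conclusion.** The point holds as a design weakness in section 5.2. The sample behind criterion 3 has no fixed size or selection, and a simple sample of a few hundred notes would probably find 0 to 2 missed VTE. That rests on about 1% VTE and 50% to 90% capture; more would be expected with higher rates and poor coding, or with many more notes. A criterion 3 result of 0% from 300 notes would be compatible with half or more of VTE being uncoded.

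Under section 3.6, made the reference standard by section 5.0, sampling by imaging status would be far more informative. The gain, for example an interval of 51% to 85% in place of 28% to 99%, applies to VTE as defined there and visible in local records. It should not be read as covering deaths without imaging or events seen elsewhere.

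**What to change.** In section 5.2:
- Use each hospital's imaging record to stratify coded-negative patients by relevant imaging within 90 days of the initial risk assessment. Relevant means any modality in section 3.6, including CT covering the named veins, whatever its reason.
- Review all of the imaged stratum, or a high, known fraction weighted by its inverse.
- Keep a random sample of stated size from the rest, for bleeding and as a check on events without local imaging.

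In section 5.3:
- Report the proportion of VTE captured by coding, with its 95% interval, primarily under the section 3.6 definitions, where non-imaged patients cannot be missed VTE.
- Report the random-sample result for the non-imaged stratum separately, with its own upper limit, and do not fold it into the main estimate.
- State that imaging or deaths elsewhere are not covered.

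The cost is one imaging query per hospital, a stratified estimate and possibly somewhat more notes. How many more cannot be settled from the documents, because the share imaged is unknown. Patient care does not change.
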